10.3 Institutional Review Board reporting requirements

10.3.1 Serious adverse drug reactions

In a subject enrolled by a UI investigator, any adverse events meeting criteria of both serious *and* attributed (possible, probable, or definite) occurring to the study agent must be reported within 10 business days to the University of Iowa Institutional Review Board. Both expected and unexpected SAE must be reported. Thus:

- Serious adverse events only
- Attributable to durvalumab (*i.e.*, drug related)
- Report to the IRB *via* HawkIRB within 10 business days of event

10.3.2 Serious adverse device effects

In a subject enrolled by a UI investigator, any adverse device effect meeting criteria of both serious and associated (possible, probable, definite) to the use of the study device must be reported within 10 business days to the University of Iowa Institutional Review Board. Both anticipated and unanticipated device effects must be reported. Thus:

- Serious adverse device effects only
- Attributable to 90Y-Theraspheres (i.e., device related)
- Report to the IRB via HawkIRB within 10 business days of effect

10.4. FDA reporting requirements [90Y TheraSphere IDE, [name], sponsor]

10.4.1 Unanticipated adverse device effects

Adverse device effects meeting criteria of serious, unanticipated, and associated (possible, probable, or definite) to 90Y-Theraspheres must be reported by the sponsor or the sponsor's appointed designee to the FDA within 10 working days of the sponsor's initial receipt of information:

- Causing **serious** adverse effect on health or safety or any life-threatening problem or death.
- **Unanticipated** adverse effects only: the effect, problem, or death was not previously identified in nature, severity, or degree of incidence in the investigational plan or application (including a supplementary plan or application)
- **Associated** with 90Y TheraSpheres with a causal relationship as described

To help the sponsor meet these reporting requirements, all unanticipated adverse device effects must be reported to the IDE sponsor **within 1 business day**. This coincides with SAE reporting requirements for the DSMC.

10.4.2 Unanticipated serious problems

The IDE sponsor will report any unanticipated serious problem associated with a device that relates to the rights, safety, or welfare of subjects within 10 working days of the sponsor's initial receipt of information. To help the sponsor meet these reporting requirements, all unanticipated problems must be reported to the IDE sponsor **within 1 business day**.

10.5. The Holden Comprehensive Cancer Center's Data and Safety Monitoring Committee [NCI]

Interventional treatment trials involving investigational agents or devices with a risk of death* (>5% or grade 4 – 5 SAE >5%), e.g. all investigator-initiated INDs, most Phase I/II trials, gene therapy, gene manipulation or viral vector systems high-risk clinical procedures if performed solely for research purposes. The use of a new chemical or drug for which there is limited or no available safety data in humans.

An independent study monitor and/or the DSMC Chair (or designee), will review study data (provided by the PI/available in OnCore) and communicate with the PI at least biannually. A copy of this communication will be forwarded to the DSMC and PRMC Chairs.

Additional reporting requirements:

- A scanned copy of the completed eligibility checklist, with screening information and PI signature, will be attached in OnCore for ongoing review by DSMC staff.

- Serious adverse events will be entered directly into an OnCore SAE report by the research team. OnCore will send an automatic notification to the DSMC Chair/acting Chair and staff for review.
- The DSMC utilizes a risk-based monitoring approach. The trial's research records will be monitored at minimum twice per year. Monitoring may be done more frequently depending on the protocol, risks to subjects, reported serious/adverse events, patient population and accrual rate. Records for a minimum of 25% of subjects will be monitored for the entire study.

Monitoring will involve the following:

- review eligibility of patients accrued to the study,
- check for the presence of a signed informed consent,
- determine compliance with protocol's study plan,
- determine whether SAEs are being appropriately reported to internal and external regulatory agencies,
- compare accuracy of data in the research record with the primary source documents,
- review investigational drug processing and documentation,
- assess cumulative AE/SAE reports for trends and compare to study stopping rules.

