The trial will be performed in **18 subjects** with mCRC with liver metastasis and the safety of immunotherapy (durvalumab) with Y90-RE will be investigated in an accelerated titration design. This would allow a maximum tolerated dose with the minimum number of subjects. At any point as noted below if there is a DLT, the study design defaults to a standard 3+3 design. Assuming a 10% loss of subjects after enrollment, the dose escalation design will require at least 9 evaluable subjects to establish the highest dose level as the maximum tolerated dose (MTD). If less than 18 subjects are administrated in the dose escalation, the rest of subjects will be administrated the MTD in the expansion cohort. **Sample size of maximum of 18 was based on an accelerated titration design and on the correlative studies including pre- and post-biopsies. The primary goal of this study is to establish safety and with a secondary goal of looking at biomarkers and other immune signals as noted.**

This study will utilize an accelerated titration design. The dose levels to which patients will be assigned in sequential cohorts are listed in the table 1.

Table 1. Dose escalation cohort of durvalumab*

		Immunotherapy (Durvalumab) Administrations						Number of Administration of Durvalumab	
Dose level	Pre-Y90 doses		Post-Y90 doses			Week2	Week4	Week6	
	Week-2	Week0	Week2	Week4	Week6				
-2					X				1
-1				X	X				2
1 (start)**	X	X							2
2	X	X		X					3
3	X	X		X	X				4
4	X	X	X	X	X				5

* Please note: As noted above, the rationale for the proposed dosing schema is keeping in mind the timing of toxicities that are typically seen post Y90-RE. Most patients have elevation of their liver enzymes the first 1-2 weeks. Therefore, with the dosing escalation, we did not include the added dose at week 2 for the first dose escalation (dose level 2). Patients get fixed dosing of immunotherapy, which is the case for all immunotherapy-based studies. Depending on the dose level, patients can get a maximum of 2 doses before and 3 doses post Y90-RE (dose level 4).

**While dose level 1 and dose level -1 have the same number of durvalumab administrations, they are different since dose level 1 get 2 doses pre-Y90-RE ('priming doses of immunotherapy before Y90-RE) while dose level -1 only get 2 doses post-Y90-RE.

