A single patient will be treated per dose level until the first DLT is recorded. Once the first DLT is recorded, two additional patients are treated at the same dose level and the trial reverts to a standard 3+3 design. At which time, decisions on when and how to dose escalate are described below.

Number of patients with DLT at a given dose level	Decision Rule
0 out of 3	Enter 3 patients at the next higher dose level
1 out of 3	Enter up to 3 additional patients at the same dose level. 
 • If 0 of these 3 patients experience DLT, proceed to the next dose level. • If 1 or more of these 3 patients experience DLT, then dose escalation is stopped, and this dose is declared the maximally administered dose. Three (3) additional patients will be entered at the next lowest dose level if only 3 patients were treated previously at that dose.
≥ 2 out of 3	Dose escalation will be stopped. This dose level will be declared the maximally administered dose. Three (3) additional patients will be entered at the next lowest dose level if only 3 patients were treated previously at that dose.

Up to 6 patients will be treated at each dose level. The MTD will be defined as the highest dose level for which at most 1 out of 6 patients experience a DLT. If DLT meets the stopping boundaries set by the above dose algorithm at dose level 1 (for example, more than 1 out of 3 or more than 1 out of 6 patients), the next cohort of 3 patients will be entered at the dose level of -1. If dose level -1 meets the stopping boundaries, the next cohort of 3 patients will be entered at dose level -2.

If an MTD is determined, an expansion cohort using the RP2D will be carried out in additional patients for a maximum of 18 patients. If an MTD is not determined, the expansion cohort will utilize the dosing scheme from cohort 4.

After the end of treatment visit (EoT) subjects (if applicable) are to resume the previously discontinued chemotherapy until all cycles have been administered or treatment is discontinued as per regular standard of care or secondary resection if deemed a candidate. The decision to resume the previously discontinued chemotherapy is to be done at investigators discretion. As the patients will commence a different treatment regime, no active follow-up will be done as part of this study other than progression free survival and overall survival.

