17.0 Statistical Considerations and Methodology

17.1 Study Design

This is a single arm phase I study designed to determine the maximally tolerated dose (MTD) and toxicity profile of Yttrium-90 radioembolization combined with immunotherapy in the treatment of liver-predominant, metastatic colorectal cancer using the accelerated titration design.

Once the MTD is reached, if total accrual is less than 18, additional patients will be enrolled in an expansion cohort to reach full accrual of 18 patients.

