17.2 MTD Definition and Determination

For this protocol, the patient must return to clinic for evaluation at least every **14** days +/- 5 days. Patients will be treated and observed for a minimum of **8** weeks post-Y90-RE before new patients are treated. Doses will not be escalated in any individual patient.

MTD Definition: The MTD will be defined as the highest dose level for which at most 1 out of 6 patients experience a dose-limiting toxicity (DLT). A total of 6 patients treated at the MTD will be sufficient to identify common toxicities at the MTD. For instance, those toxicities with an incidence of at least 25% will be observed with a probability of at least 82% (1-(1-0.25)⁶).

Refer to Section **7.42** for definition of dose-limiting toxicity (DLT).

MTD Determination:

This study will utilize an accelerated titration design. The dose levels to which patients will be assigned in sequential cohorts are listed in the table below.

		Immunotherapy (Durvalumab) Administrations					
		Pre-Y90 doses		Post-Y90 doses		Number of Administration of Durvalumab	
Dose level	Week -2	Week 0	Y90-Radio-embolization	Week 2	Week 4	Week 6	
					X		1
-2					X		2
-1							2
1 (start)	X	X					3
2	X	X		X			4
3	X	X		X	X		5
4	X	X		X	X	X	

In the first phase, a single patient will be treated per dose level until the first DLT is recorded. Once the first DLT is recorded, two additional patients are treated at the same dose level and the trial reverts to a standard 3+3 design in the second phase. At which time, decisions on when and how to dose escalate are described below.

Number of patients with DLT at a given dose level	Decision Rule
0 out of 3	Enter 3 patients at the next higher dose level
1 out of 3	Enter up to 3 additional patients at the same dose level. 
 • If 0 of these 3 patients experience DLT, proceed to the next dose level. • If 1 or more of these 3 patients experience DLT, then dose

	escalation is stopped, and this dose is declared the maximally administered dose. Three (3) additional patients will be entered at the next lowest dose level if only 3 patients were treated previously at that dose.
≥2 out of 3	Dose escalation will be stopped. This dose level will be declared the maximally administered dose. Three (3) additional patients will be entered at the next lowest dose level if only 3 patients were treated previously at that dose.

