17.3 Sample Size

This phase I study is expected to require 9 evaluable patients to establish the highest dose level as the MTD. We do not expect serious adverse events or DLTs based on experience of treating patients with Y90-RE. Experience with immunotherapy as well has been reassuring from a safety perspective. Anecdotally, we have had some patients who were on immunotherapy for HCC, which got FDA approved in October 2017 who got Y90-RE with no untoward side effects and good responses. Given the clinical experience and data that is available so far, we do not expect to reach the maximum accrual dictated by budget restrictions during the MTD determination portion of the study. Once the MTD is determined, additional patients will be accrued in an expansion cohort in order to reach full accrual of 18 patients between Phase I and the expansion cohort.

The primary objective of the expansion cohort is to evaluate whether Y90-RE in combination with durvalumab confers an immune response (mechanism of action) irrespective of dose level as estimated by the change in frequency of immune cells pre- and post-treatment. A sample size of 18 patients will allow the sample mean for the pairwise difference to be estimated with a 95% confidence interval half-width of 0.5 SD.

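### The documents give no DLT boundary for the expansion cohort, half of the 18 patients on the plan's expected course, although monitors are told to compare events with stopping rules

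*Combined protocol and SAP*

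**What the plan says.** **Escalation.** Under section 17.2, "a single patient will be treated per dose level until the first DLT is recorded"; after that a 3+3 scheme applies, with up to 6 patients per level. "The MTD will be defined as the highest dose level for which at most 1 out of 6 patients experience" a DLT. The stopping boundaries described in 1.4.6 and 17.2 belong to this algorithm.

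**Size of escalation.** Section 17.3: "This phase I study is expected to require 9 evaluable patients to establish the highest dose level as the MTD". Section 1.4.6 words the same figure as a minimum: "the dose escalation design will require at least 9 evaluable subjects to establish the highest dose level".

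**Expansion.** Section 17.1 says that once the MTD is reached, "additional patients will be enrolled in an expansion cohort to reach full accrual of 18 patients". Section 1.4.6 adds: "If an MTD is not determined, the expansion cohort will utilize the dosing scheme from cohort 4". Section 17.3 gives the expansion an immune-response objective and attaches no DLT rule to it.

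**Monitoring.** Section 10.5 has monitors "assess cumulative AE/SAE reports for trends and compare to study stopping rules". Serious adverse events (10.5.3) and DLTs (10.5.5) are reported within 1 business day, and data are reviewed at least twice a year. Section 10.0 refers to a detailed monitoring plan on file with the committee and the IRB, and to an abbreviated appendix copy. No such appendix is in the contents list or the supplied text.

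**The concern.** Section 10.5 relies on stopping rules, but the only ones to be found end when escalation ends. From then on, no stated number of DLTs pauses accrual, reopens the dose decision or changes the recommendation. Safety is the primary goal (2.1.1), the RP2D is a stated objective (2.2.2), and section 1.4.1 describes this as the first trial of the combination. A level that passed six patients by chance could be given to all remaining patients and then recommended, with no pre-stated point at which the committee must decide whether to go on.

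**Working it through.** **1. The plan's own figures.** With no DLT, levels 1 to 3 take one patient each and level 4 takes six: 1 + 1 + 1 + 6 = 9, which matches sections 1.4.6 and 17.3. The expansion is then 18 − 9 = 9 patients, or 50%. Section 17.2's 82% chance of seeing a 25% toxicity in six patients also reproduces: 1 − 0.75^6 = 0.822.

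**2. The other reading.** Four single patients without a DLT do not meet an MTD definition that refers to six. If the fallback sentence in 1.4.6 then opens the expansion at level 4, escalation used 4 patients and the expansion is 18 − 4 = 14 (78%). That conflicts with the 9-patient figure.

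**3. How weak a filter six patients are.** P(at most 1 DLT in 6) = (1 − p)^6 + 6p(1 − p)^5.
- p = 0.30: 0.118 + 0.303 = 0.42
- p = 0.40: 0.047 + 0.187 = 0.23

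The exact 95% interval for 1 of 6 is 0.4% to 64%.

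**4. What could follow with no boundary.** Nine expansion patients at a 40% rate have 9 × 0.40 = 3.6 expected DLTs, and P(at least 3 of 9) = 77%. On the second reading, four clean patients occur with probability 0.7^4 = 0.24 at a flat 30% rate. The 14 who follow have 14 × 0.30 = 4.2 expected DLTs.

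**5. An illustrative boundary.** Count all patients at the expansion dose and pause accrual at 2 or more DLTs within the first 6, 4 or more by 12, or 5 or more by 15. Check after each patient. These are exact binomial recursions, starting either from 0 or 1 DLT in six patients or from one clean patient at level 4:

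| True DLT rate | Pause, after six patients | Pause, four-clean path |
|---|---|---|
| 10% | 1% | 9% |
| 17% | 5% | 24% |
| 30% | 27% | 61% |
| 40% | 52% | 84% |

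A 40% level passes six patients and then survives the boundary with probability 0.233 × (1 − 0.521) = 0.11, against 0.23 with no boundary. On the four-clean path at 30%, about 8.7 of the 14 are treated, with 2.6 DLTs instead of 4.2.

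**6. How often the expansion reaches half.** Simulating the written rules on the six-at-level-4 reading with assumed flat DLT rates, 9 patients reach expansion in 94% of trials at a 2% rate, 68% at 10% and 35% at 25%.

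**The case against.** The strongest reply is that oversight does not end with escalation, and most of it stands. The Study Chair is contacted as soon as a DLT occurs (7.4.1.2), DLTs and serious events reach the committee within 1 business day, monitoring can be made more frequent if events warrant, and toxicity is tabulated by dose level for all patients (17.5.1, 17.5.2). A reader might infer that the MTD stands whatever happens in the expansion. The documents do not say so. They are silent on how expansion DLTs bear on the RP2D, and the committee may act at its discretion.

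A reader might also infer that no stopping rule exists at all. That cannot be shown, because the monitoring plan on file may contain one.

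Nor is it established that 14 patients follow a single patient at level 4. Two sections give 9 patients, and 17.2 speaks of six treated at the MTD, so this is an ambiguity to resolve. Half of the patients in expansion is likewise the low-toxicity course; DLTs during escalation shrink the cohort, as step 6 shows.

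The example boundary has limits too. Beyond six patients it is looser than the plan's 1 in 6, tolerating 3 of 12 (25%) and 4 of 15 (27%). After an MTD from six patients its first limit adds nothing, and it then catches a 30% level only about a quarter of the time.

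What survives is narrow: reporting and review are not a threshold, and section 10.5 points to rules that the supplied documents do not define for the expansion.

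**Conclusion.** The concern holds as a missing numeric rule. On the plan's expected course, 9 of 18 patients are treated in an expansion with no stated DLT count that pauses accrual or revises the MTD or RP2D. The fallback sentence in 1.4.6 could raise this to 14 of 18, against the plan's own 9-patient figure. A 40%-toxic level enters expansion after six patients with probability 23%, and a 30%-toxic level with probability 42%. An accrual-pause rule of the kind shown would about halve the first figure, to 11%.

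The true DLT rates are assumptions; the plan expects no DLTs. The boundary results assume independent patients with a common DLT rate, and that each DLT is known before the next patient is treated. The latter fits section 17.2's 8-week observation before new patients are treated. If expansion patients were enrolled in parallel, the gain would be smaller. The finding concerns the supplied documents only.

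**What to change.** 1. In section 17.2, state a cumulative DLT boundary over all patients at the expansion dose that pauses accrual for committee review, and refer to it from 10.5. The limits of 2 in the first 6, 4 by 12 and 5 by 15 are an illustration; the sponsor should set the final numbers. If the monitoring plan on file already has a rule, state or cite it.
2. Base the MTD and RP2D conclusion on all patients treated at that dose, including the expansion.
3. Reconcile sections 1.4.6, 17.2 and 17.3 on how many patients level 4 needs before expansion opens. Say also whether the 8-week observation applies patient by patient in the expansion.

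The cost is protocol wording and no extra patients. The downside is an unneeded pause: about 1% (after six patients) to 9% (four-clean path) at a true 10% DLT rate, and 5% to 24% at 17%, roughly the plan's own 1-in-6 limit. The action is a pause for review, so a false alarm costs time and does not by itself close the cohort.

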10.5.1 Routine Adverse Event Reporting Requirements

An adverse event (AE) is defined in the *CTEP, NCI Guidelines* [2005] as “any unfavorable and unintended sign (including an abnormal laboratory finding), symptom or disease temporally associated with the use of a medical treatment or procedure (attribution of unrelated, unlikely, possible, probably or definite).” Routine adverse events occurring in study subjects are captured in OnCore, the clinical trials management system, for review and assessment by the P.I. and IDE sponsor as well as the DSMC.

10.5.2 Routine Adverse Device Effect Reporting Requirements

An adverse effect is defined by FDA as “Any adverse medical occurrence that may or may not be related to the investigational device.” All adverse effects occurring in study subjects will be captured in OnCore, the clinical trials management system, for review and assessment by the P.I. and IDE sponsor as well as the DSMC.

10.5.3 Serious Adverse Events

Any experience or condition meeting the definition of a serious adverse event (SAE; 21CFR312.32) occurring in a study subject from the first day of study treatment and typically continue through the 30-day follow-up period after treatment is discontinued will be captured. Investigators **must** report to the DSMC any SAE, regardless of attribution to study drug. SAEs must be reported *via* an OnCore SAE Report \leq 1 business day of learning of the event.

10.5.4 Unanticipated Device Effects

Any experience or condition meeting the definition of an unanticipated adverse device effect (UADE) in a study subject (SAE; 21CFR812.3(s)), from the first day of study treatment and typically continue through the 30-day follow-up period after treatment is discontinued will be captured. Investigators **must** report to the DSMC any unanticipated adverse device effect *via* an OnCore SAE Report \leq 1 business day of learning of the effect.

10.5.5 Dose limiting Toxicities

Any adverse event meeting the criterion of a dose limiting toxicity will be reported *via* an OnCore SAE Report \leq 1 business day of learning of the event or from determining the event met DLT criteria.

10.6 Principal Investigator Reporting Requirements

As per 21CFR812.50, the principal investigator shall prepare and submit the following complete, accurate, and timely reports to the IDE Sponsor of 90Y TheraSpheres ([name], MD):

- **Withdrawal of IRB approval.** An investigator shall report to the sponsor, within 5 working days, a withdrawal of approval by the reviewing IRB of the investigator's part of an investigation.
- **Annual Progress Report.** An annual progress reports on the investigation to the sponsor, the monitor, and the reviewing IRB at regular intervals, but in no event less often than yearly.
- **Deviations from the investigational plan.** An investigator shall notify the sponsor and the reviewing IRB (see §56.108(a) (3) and (4)) of any deviation from the investigational plan to protect the life or physical well-being of a subject in an emergency. Such notice shall be given as soon as possible, but in no event later than 5 working days after the emergency occurred. Except in such an emergency, prior approval by the sponsor is required for changes in or deviations from a plan, and if these changes or deviations may affect the scientific soundness of the plan or the rights, safety, or welfare of human subjects, FDA and IRB in accordance with §812.35(a) also is required.
- **Informed consent.** If an investigator uses a device without obtaining informed consent, the investigator shall report such use to the sponsor and the reviewing IRB within 5 working days after the use occurs.
- **Final report.** An investigator shall, within 3 months after termination or completion of the investigation or the investigator's part of the investigation, submit a final report to the sponsor and the reviewing IRB.
- **Other.** An investigator shall, upon request by a reviewing IRB or FDA, provide accurate, complete, and current information about any aspect of the investigation.

